5.4 Efficacy variables

5.4.1 Molecular response

Scaling towards an international standard will be performed for all molecular results using laboratory specific conversion factors. In this process, the raw ratio between BCR-ABL and the control gene ABL is calculated and multiplied by the lab-specific conversion factor ([Branford and Hughes 2006]). Therefore, using the international unit, the BCR-ABL ratio will be presented in %. The MRDx assay using PAXgene™ Blood RNA tubes from MMD laboratory will be used in this study. The lab conversion factor for this assay was 1.1 until 1 June 2020 and 1 thereafter.

The BCR-ABL ratio in IS % is calculated by multiplying the raw BCR-ABL ratio with the lab-specific conversion factor and then by 100:

$$\text{BCR-ABL ratio (in \%)} = (\text{BCR-ABL} / \text{ABL}) * \text{conversion factor} * 100$$

The BCR-ABL ratio in IS% provided by the central laboratory will be use in the analyses. However, to calculate the fold change in BCR-ABL1/ABL used to derive the loss of MMR criteria, in case the BCR-ABL number of copies is reported as a 0 value and the patient doesn't have atypical transcript at baseline, then the value will be replaced by 1, and the BCR-ABL ratio will be calculated.

Molecular response is categorized as follows:

- 10% > BCR-ABL ratio
- 1% < BCR-ABL ratio ≤ 10%
- 0.1% < BCR-ABL ratio ≤ 1%
- 0.01% < BCR-ABL ratio ≤ 0.1%
- 0.0032% < BCR-ABL ratio ≤ 0.01%
- BCR-ABL ratio ≤ 0.0032%

Major molecular response (MMR)

Major molecular response (MMR) is defined as a value of ≤ 0.1% of BCR-ABL ratio on the IS. This endpoint corresponds to a ≥ 3 log reduction in BCR-ABL transcripts from a standardized baseline value for untreated CML patients which was established in the IRIS study (STI5710106). MMR will be considered as a binary variable with patients achieving MMR

grouped as ‘responders’ and patients not achieving MMR or patients with missing PCR evaluations grouped as ‘non-responders’.

Loss of MMR

Loss of MMR is defined as an increase in BCR-ABL1/ABL to $> 0.1\%$ by international scale (IS) in association with a ≥ 5 -fold rise in BCR-ABL1/ABL from the lowest value achieved up to that time point on study treatment and replicated by a second analysis of the same sample. Loss of MMR must be confirmed by a subsequent sample analysis within 4-6 weeks showing loss of MMR associated with a ≥ 5 -fold rise in BCR-ABL1/ABL from the lowest value achieved up to that time point on study treatment.

If there is any assessment in between indicating a BCR-ABL ratio of $\leq 0.1\%$ or a < 5 -fold increase in BCR-ABL ratio from the lowest value achieved up to that time point on study treatment, then the initial indication of loss of MMR cannot be confirmed. However, an assessment indicating (unconfirmed) loss of MMR will be considered as confirmed loss of MMR if the patient had loss of CHR or loss of complete cytogenetic response (CCyR) after the achievement of MMR. CML-related death or progression to AP or BC will be considered as confirmed loss of MMR in any case (if they occurred on treatment) (given that the patient achieved prior MMR).

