2.7.1 Secondary endpoints

2.7.1.1 Molecular response

MMR rates at all scheduled data collection time points, i.e., the protocol-planned visits except for 24 weeks and 96 weeks which are already covered by primary and key secondary endpoints. Such rates are defined as the proportion of patients with MMR at the respective time points.

MMR rates by all scheduled data collection time points, i.e., the protocol-planned visits. These are cumulative MMR rates by time points and are defined as the proportion of patients who achieve MMR at or before specified visits, i.e. if a patient achieves an MMR but then loses it before or at a specific visit, he/she will still be classed as achieving MMR by that specific time point.

Molecular response category at specific time points, i.e., the protocol-planned visits. Categories of molecular response are defined in Appendix.

Molecular response category by specific time points, i.e., the protocol-planned visits. This is defined as the best (lowest) molecular response category up to the specific time points.

Time to MMR (in weeks) is defined as: (date of first documented MMR - date of randomization + 1)/7.

Duration of MMR is defined for patients in the MMR Responder Set as the time between the date of the first documented MMR and the end date of MMR, i.e. the earliest date of confirmed loss of MMR, progression to accelerated phase (AP)/blast crisis (BC), or CML-related death.

Loss of MMR and progression to accelerated phase (AP)/blast crisis (BC) are defined in Appendix.

For patients for whom none of the events above is reported, the duration will be censored (see [Section 2.7.3](#)). The duration of MMR (in weeks) is calculated as: (end date or censoring date of MMR - date of first MMR + 1)/7.

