5.5 Derivation of response rates and categories

5.5.1 Response rate at a specific time point

The molecular and cytogenetic response evaluations will be summarized by the following mutually exclusive categories which are based on the respective assessment within the time window:

- **Response categories** (sections 5.4.1 and 5.4.2): Patients with an available assessment at that time point (+/- time window) indicating any of the response categories.
- **No response:** Patients with assessment at that time point (+/- time window) indicating 'no response'
- **Missing:** Patients without an evaluable response assessment at that time point (+/- time window). This category is then further split into patients who are ongoing without treatment failure at the beginning of the relevant time window, patients who are ongoing with treatment failure at the beginning of the relevant time window, patients who discontinued due to lack of efficacy, disease progression (PD) or death and patients who discontinued due to other reasons.

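### SAP section 5.4.1 sets no sensitivity condition for zero-copy PCR samples, so deep molecular response percentages can be overstated; the top response category is also misprinted

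*Combined protocol and SAP*

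**What the plan says.** The operative text is section 5.4.1 of the current SAP (addendum 1.0); amendment 3 has the same wording.

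- **Source of the ratio.** "The BCR-ABL ratio in IS% provided by the central laboratory will be use in the analyses".
- **Formula.** "The BCR-ABL ratio in IS % is calculated by multiplying the raw BCR-ABL ratio with the lab-specific conversion factor and then by 100". On the factor: "The lab conversion factor for this assay was 1.1 until 1 June 2020 and 1 thereafter".
- **Deepest category.** The last line of the category list reads "BCR-ABL ratio ≤ 0.0032" per cent. It has no lower bound and no condition on the ABL copy number.
- **Zero-copy rule.** Zero is replaced by 1 "in case the BCR-ABL number of copies is reported as a 0 value", provided the patient has no atypical transcript at baseline. The rule serves only "to calculate the fold change in BCR-ABL1/ABL used to derive the loss of MMR criteria".
- **Use of the categories.** Section 2.7.2 reports frequency and percentage of each category by arm on the FAS, at and by each time point. For the cumulative version, section 2.7.1.1 says: "This is defined as the best (lowest) molecular response category up to the specific time points".
- **Non-evaluable samples.** Section 5.5.1 assigns the Missing category to "Patients without an evaluable response assessment at that time point", but the SAP does not define evaluable for a PCR sample. Cytogenetics, by contrast, has a minimum of 20 metaphases (section 5.4.2).
- **Top category.** The first line of the list is printed as `10% > BCR-ABL ratio`.

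**The concern.** A result of zero copies only shows that the ratio is below what the sample could detect, and that limit depends on how many ABL copies were amplified. Read literally, section 5.4.1 gives every zero-copy sample a ratio of 0% and therefore the deepest category. The same sample is treated as 0 copies for the category and as 1 copy for the loss-of-MMR nadir. The SAP's other below-detection rules use the limit: laboratory values reported as below X are set to X (section 5.3), and marrow blast percentages below X are set to X in summary tables (section 5.4.2).

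The cumulative summary keeps the best category ever reached, so one insensitive sample is enough to hold a patient in the deepest category at all later time points. At stake are the descriptive percentages at ≤ 0.01% and ≤ 0.0032%, including the category tables planned for the Japan subgroup.

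The top category is a separate slip. As printed, it covers everything below 10%, overlaps the five categories beneath it and leaves ratios above 10% with no category, although section 5.5.1 calls for mutually exclusive categories.

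**Working it through.** **Inputs from the SAP.** The ratio formula, the factors 1.1 and 1, and the category limits 0.0032%, 0.01% and 0.1% (section 5.4.1). The SAP states no ABL copy number, so the ABL counts below are assumptions. The only related figure to reproduce is in the 2017 SAP, Table 5-3, which pairs ≤ 0.0032% with a 4.5-log reduction: 100 × 10^(−4.5) = 0.00316%, which agrees.

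**Step 1: zero copies.** 0/ABL × factor × 100 = 0% for any ABL count above zero. The sample is therefore classed ≤ 0.0032% at 500 copies just as at 100,000.

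**Step 2: what a sample can show.** Taking one copy as the detection limit, the limit is factor × 100 / ABL, so the smallest ABL count that supports a threshold is factor × 100 / threshold (in %).

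| Threshold | Factor 1 | Factor 1.1 |
|---|---|---|
| ≤ 0.0032% | 31,250 | 34,375 |
| ≤ 0.01% | 10,000 | 11,000 |
| ≤ 0.1% (MMR) | 1,000 | 1,100 |

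For example, with factor 1.1 the limit is 0.011% at 10,000 ABL copies and 0.0055% at 20,000. A zero-copy sample at those counts could support only the 0.01–0.1% and 0.0032–0.01% categories respectively.

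**Step 3: how often zero copies would occur.** With Poisson sampling, P(0) = exp(−ABL × (ratio/100) / factor). For a true ratio of 0.01% and factor 1.1:

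| Assumed ABL copies | Expected BCR-ABL copies | P(0) per sample | At least one zero in 5 samples, 1 − (1 − P(0))^5 |
|---|---|---|---|
| 10,000 | 0.909 | 40% | 92% |
| 20,000 | 1.818 | 16% | 59% |
| 30,000 | 2.727 | 6.5% | 29% |
| 50,000 | 4.545 | about 1% | about 5% |

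The last column needs a patient to stay at exactly 0.01% for five independent samples, so it illustrates accumulation and does not forecast it. The 50,000 row lies above the Step 2 threshold. There the limit is 0.0022%, and the remaining 1% is ordinary sampling error that no detection-limit rule removes.

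**Step 4: the top category.** A ratio of 5% satisfies both `10% > BCR-ABL ratio` and the 1–10% line. A ratio of 20% satisfies none of the six lines.

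**The case against.** The strongest counter-argument is that the SAP uses the ratio supplied by the central laboratory, and the laboratory's reporting rule for a low-ABL or undetected sample is not given. It might report no result or a value below a limit. Protocol section 7.2.1.1 (Molecular response), which was not in the part of the document available for this review, is a natural place for a minimum ABL count. The undefined word evaluable in section 5.5.1 also leaves room to reject poor samples. This stands: it limits the conclusion to what section 5.4.1 allows and rules out a statement about what will happen.

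A reader might take the replacement of 0 by 1 as an admission that zero is not a real value. The text does not support that. A fold rise from zero is undefined, so the rule is needed arithmetically and says nothing about sensitivity.

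It is also fair that the effect shrinks quickly as ABL rises, that deep response is not an endpoint in Table 1-1, and that section 2.7.2 plans no test, confidence interval or between-arm difference for these categories. Patients enter with ratios of at least 1%, or above 0.1% if intolerant, and there are only five post-baseline PCR windows up to week 24. Repeated zeros at a steady 0.01% are therefore implausible at the primary analysis. These points reduce the importance but do not supply the missing rule.

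Finally, the intent of the top category is obvious. It is still an operative definition and should be printed correctly.

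**Conclusion.** The gap is real on the SAP text. Followed as written, section 5.4.1 puts a zero-copy sample with fewer than 31,250 (factor 1) or 34,375 (factor 1.1) ABL copies into a category that the sample cannot demonstrate. The descriptive deep-response percentages can therefore be overstated, provided that no laboratory or protocol rule already screens such samples. The ≤ 0.01% level is exposed only below 10,000 to 11,000 copies. The number of affected samples is unknown, and the per-sample range of 40% down to about 1% rests on assumed ABL counts and one assumed true ratio.

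Two stronger readings are tempting. One is that the between-arm difference in deep response is exaggerated. That would require the arms to differ in low-level disease, which the plan cannot tell us, and no such difference is a planned estimate. The other is that the primary or key secondary result is at risk. MMR would be affected only by zero-copy samples below 1,000 to 1,100 ABL copies, so it is practically untouched, and the sample size does not depend on this.

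The misprinted top category is a definite error that needs no assumption.

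**What to change.** In section 5.4.1, for the response categories, do one of two things:

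- class a zero-copy sample by its detection limit, factor × 100 / ABL copies, so that it enters ≤ 0.0032% only if that value is ≤ 0.0032%; or
- cite an existing minimum ABL count that supports each category. For the deepest category it would have to be about 31,250 to 34,375.

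State also how zero-copy results are classed in patients with an atypical transcript at baseline. The existing replacement rule excludes them, the categories do not, and the protocol's own amendment rationale says that measurement on the international scale is possible only for typical transcripts.

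Separately, change the first category to BCR-ABL ratio > 10%, so that the list is exhaustive and mutually exclusive.

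The cost is SAP wording and one derivation line, using copy numbers that section 5.4.1 already handles. The detection-limit option is conservative: some patients with truly undetectable disease but low ABL counts will be moved out of the deepest category, so deep-response rates will be slightly lower. The rule can be applied at the 96-week analysis, with the 24-week category tables rerun as a check.

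### The top molecular response band in SAP section 5.4.1 has its inequality reversed, so ratios above 10% have no defined band in the descriptive category tables

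*Combined protocol and SAP*

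**What the plan says.** Section 5.4.1 of the SAP (addendum 1, with identical wording in amendment 3) sets out the molecular response bands. The first is "10% > BCR-ABL ratio". The second is "1% < BCR-ABL ratio ≤ 10" (per cent), three further bands step down by the same construction, and the last is "BCR-ABL ratio ≤ 0.0032" (per cent).

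Sections 2.7.1.1 and 2.7.2 send the reader to the Appendix for these categories and tabulate them on the FAS, both at and by each scheduled time point. For the by-time-point version, section 2.7.1.1 adds: "This is defined as the best (lowest) molecular response category up to the specific time points".

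Section 5.5.1 sorts patients at a time point into those in a response category, those with no response, and those missing. For molecular response it does not say which ratio counts as no response.

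**The concern.** The list runs from the highest ratios to the lowest, so its first row should hold everything above the second row's ceiling of 10%. With the sign as printed it holds everything below 10% instead. A programmer who follows the text exactly has nowhere to put a patient above 10%, and finds two bands for almost everyone else.

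Ratios above 10% are a real group in this trial. Section 5.4.4 makes a ratio above 10% IS a treatment failure criterion at six and at 12 months, and section 5.1.2.1 uses 10% as the cut for imputing baseline major cytogenetic response. At stake is the readability of the category tables: the row that should show the least responsive patients would not be defined. The same list serves the Japan subgroup tables in section 2.2.1 and the later analyses in section 2.15.

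**Working it through.** The plan gives no figure to reproduce here; the check is one of logic. Let r be the BCR-ABL ratio in % IS.

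**Inputs (section 5.4.1).** A: 10 > r. B: 1 < r ≤ 10. C: 0.1 < r ≤ 1. D: 0.01 < r ≤ 0.1. E: 0.0032 < r ≤ 0.01. F: r ≤ 0.0032.

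**Bands met by selected ratios.**

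| r (%) | As written | With A as r > 10 |
|---|---|---|
| 0 | A and F | F |
| 0.005 | A and E | E |
| 0.05 (MMR) | A and D | D |
| 0.5 | A and C | C |
| 5 | A and B | B |
| 10 | B | B |
| 10.01 | none | A |
| 50 | none | A |

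Over 0% and a log-spaced grid from 0.0001% to 100%, all 50,001 values below 10% met two bands and all 10,000 values above 10% met none. Exactly 10% met one. With the sign corrected, every value met exactly one.

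**Tables at a time point.** Let a, b, c and m be the shares of the FAS with r below 10%, exactly 10%, above 10% and missing, so a + b + c + m = 1. Following the text literally, the six bands plus Missing sum to 2a + b + m = 1 + a − c. The total is too high by the share below 10%, offset by the omitted share above 10%.

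**Tables by a time point.** Each patient contributes one best category. If bands rank in list order, a patient whose best ratio is 0.05% goes to D and one at 5% goes to B, each counted once, and A stays empty. Let c′ be the share whose best ratio so far is above 10%. The total is then 1 − c′, so the only fault is omission. Because section 5.5.2 keeps patients in these tables after discontinuation, someone who never reached 10% or below stays without a band at every later time point.

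**Could another section supply the missing band?** The 'No response' group in section 5.5.1 is the only candidate. For cytogenetic response, section 5.4.2 gives an explicit None category (more than 95% up to 100% Ph+). For molecular response there is no counterpart. If ratios above 10% were placed there anyway, the at-time-point total would become 2a + b + c + m = 1 + a: the omission would be gone, but the overlap would remain.

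**What uses a different cut.** MMR is r ≤ 0.1 (sections 2.5.1, 2.6.1 and 5.4.1). Treatment failure, and so time to treatment failure, states its own correctly written cut of more than 10% (section 5.4.4). The sample size rests on MMR rates of 15% and 35% (section 3.1). None of these uses band A.

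**The case against.** The best defence is that this is an evident slip. The list descends and the second row stops at 10%, so a careful programmer would code the first row as above 10%. That stands, and it keeps the point small. It does not make the text right: this is the derivation rule itself, and both SAP versions print it the same way.

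It can also be said that section 5.5.1 does not demand disjoint bands. Its phrase "mutually exclusive categories which are based on the respective assessment within the time" window introduces the three groups (response categories, no response, missing), not the bands inside the first. The cytogenetic list beside it overlaps by design, since major response is complete plus partial. That is fair, and the point does not rest on that phrase. The gap above 10% and the reversed sign are visible in section 5.4.1 alone.

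A third argument is that 'No response' may have been meant to hold ratios above 10%. This is possible but unstated, and it would leave the overlap in place.

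A reader might also infer that the error removes failing patients from the analysis. The documents do not support that: failure is derived separately. In addition, section 2.1.1 stops FAS efficacy summaries at treatment failure, so beyond six months few ratios above 10% would reach the at-time-point tables apart from the failure assessment itself.

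**Conclusion.** The point holds as a wrong sign in an operative derivation rule, with a small effect. Taken literally, every ratio above 10% lacks a defined band in both kinds of table, and every ratio below 10% meets two bands in the at-time-point tables only.

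Two wider readings are not supported. Percentages do not exceed 100% in all tables by the share of patients below 10%: the best-category rule prevents double counting in the by-time-point tables, and elsewhere the omitted patients offset part of the excess. Nor can the baseline molecular response summary be said to be wrong, because section 2.3 does not say that it uses these bands, although no other set is defined.

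The affected output is descriptive and carries no confirmatory test. The conclusion assumes that addendum 1, the latest SAP body available, is current; a further SAP history follows it without its text. It also assumes that the bands rank in list order.

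**What to change.** Replace the first bullet of section 5.4.1 with: BCR-ABL ratio > 10%. The six bands then cover every ratio exactly once. Check that the programs, row labels and footnotes of the molecular response category tables use this definition, including any already produced for the 24-week analysis and the Japan subgroup. It would help to add a clause saying that the 'No response' group in section 5.5.1 does not hold molecular ratios above 10%. The cost is one or two lines of SAP text and a short program check, with no change to design, data collection, sample size or inference.

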2.7.1.2 Cytogenetic response

At each assessment time point the cytogenetic response status of each patient is classified as complete, partial, major, minor, minimal response and none (a review of a minimum of 20 metaphases is required):

- Complete response (CCyR): 0% Philadelphia chromosome positive (Ph+) metaphases
- Partial response (PCyR): >0 to 35% Ph+ metaphases
- Major response (MCyR = CCyR + PCyR): 0 to 35% Ph+ metaphases
- Minor response (mCyR): >35 to 65% Ph+ metaphases
- Minimal response: >65 to 95% Ph+ metaphases
- None: >95 to 100% Ph+ metaphases.

As per protocol, bone marrow aspirate for cytogenetic analyses will be performed as long as subjects have not achieved MMR. Therefore, in case no bone marrow aspirate was performed but the subject is in MMR at a specific time-point, the subject is considered to have achieved CCyR at that time-point. The date of CCyR is imputed by the date of MMR at the same scheduled time-point.

CCyR rates at all scheduled data collection time points, i.e., the protocol-planned visits. Such rates are defined as the proportion of patients in CCyR at the respective time points among patients in the CCyR Analysis Set, which excludes patients who are in CCyR at baseline.

CCyR rates by all scheduled data collection time points, i.e., the protocol-planned visits. Such rates are defined as the proportion of patients who achieve CCyR at or before the respective time points among patients in the CCyR Analysis Set.

Cytogenetic response category at specific time points, i.e., the protocol-planned visits. At each assessment time point the cytogenetic response status of each patient is classified as complete, partial, major, minor, minimal response and none (a review of a minimum of 20 metaphase is required) as defined in Appendix.

Cytogenetic response category by specific time points, i.e., the protocol-planned visits. This is defined as the best (lowest) cytogenetic response category up to the specific time points.

Time to CCyR (in weeks) is defined for patients as: (date of first documented CCyR - date of randomization + 1)/7.

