2.7.3 Handling of missing values/censoring/discontinuations

MMR rates at specific time points: Patients discontinuing the randomized treatment prior to a specific time point due to any reason or patients without an available assessment at that time point will be considered as non-responders for that time point.

MMR rates by specific time points:

Patients without any documented response for which an evaluable response assessment was never provided will be considered as non-responders for the period of time up to that time point.

Molecular response at specific time points: The category “Missing” will be assigned to

- Ongoing cases, i.e. patients without assessment at the specific time point who have not discontinued study treatment and have not been treated sufficiently long for a specific time point
- Discontinued due to progressive disease/death prior to a specific time point
- Discontinued due to other reasons prior to a specific time point
- **Molecular response category by specific time points:** The category “Missing” will be assigned to patients for whom an evaluable response assessment was never provided.

Time to MMR: For patients in the FAS who have not experienced any MMR, the time will be censored as follows in the Kaplan-Meier analysis:

- If a patient does not achieve the specified response before the cut-off date for the analysis, censoring time will be the last molecular assessment (PCR) date on treatment prior to the cut-off date or the EoT visit, whichever comes first.
- If a patient discontinues study treatment prior to achieving a response for a reason other than disease progression or death, then the patient will be censored at the last molecular assessment (PCR) date on treatment prior to the cut-off date or the EoT visit, whichever comes first.
- If a patient discontinues study treatment prior to achieving a response due to progression or death, then the censoring time will be set to the longest follow-up time in the treatment group, that is, consider the response is impossible to reach.
- In case no on-treatment response assessment was performed, the patient will be censored at day 1.

Duration of MMR: For patients in the MMR responder set who have not experienced any event (loss of MMR, progression to AP/BC, or CML-related death), the duration will be censored at the last molecular assessment (PCR) date on treatment.

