5.4.2 Cytogenetic response

Cytogenetic response will be based on the percentage of Ph⁺ metaphases in the bone marrow. Cytogenetic evaluations will be considered for response assessment only if the number of metaphases examined is ≥ 20 in each bone marrow sample. As per protocol, fluorescent *in-situ* hybridization (FISH) assessments will not be considered for any evaluation of cytogenetic response during treatment.

Cytogenetic response is categorized as follows (a review of a minimum of 20 metaphases is required):

- Complete response (CCyR): 0% Philadelphia chromosome positive (Ph⁺) metaphases
- Partial response (PCyR): >0 to 35% Ph⁺ metaphases
- Major response (MCyR = CCyR + PCyR): 0 to 35% Ph⁺ metaphases
- Minor response (mCyR): >35 to 65% Ph⁺ metaphases
- Minimal response: >65 to 95% Ph⁺ metaphases
- None: >95 to 100% Ph⁺ metaphases.

If bone marrow aspirate blast percentage is provided as ‘ $<X$ ’ (i.e. below limit of detection), the numeric value is set to X for summary tables. In the listing ‘ $<X$ ’ will be presented.

Complete cytogenetic response (CCyR)

CCyR is defined as a value of 0% Ph⁺ metaphases in bone marrow.

CCyR will be considered as a binary variable with patients achieving CCyR grouped as ‘responders’ and patients not achieving CCyR, patients with missing cytogenetic evaluations grouped as ‘non-responders’.

Loss of CCyR

Loss of CCyR is defined as an increase in the Ph+ bone marrow cells to > 0%.

Loss of CCyR must have led to treatment discontinuation because of lack of efficacy (based on the “End of Treatment Phase Disposition” eCRF or “End of Treatment Disposition” eCRF during the Treatment switch phase with Subject status=“lack of efficacy” and Reason of treatment failure = “After start of therapy, loss of CHR, CCyR or PCyR”).

In addition, CML-related death or progression to AP or BC will be considered as loss of CCyR in any case (if they occurred on treatment).

Major cytogenetic response (MCyR)

MCyR is defined as a value of 0% to 35% Ph+ metaphases in bone marrow.

MCyR will be considered as a binary variable with patients achieving MCyR grouped as ‘responders’ and patients not achieving MCyR, patients with missing cytogenetic evaluations grouped as ‘non-responders’.

Loss of MCyR is defined as an increase in the Ph+ bone marrow cells to > 35%. For patients with response = PCyR, this would constitute loss of PCyR.

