5.4.4 Treatment Failure

The following events will constitute 'treatment failure', and are based on the ELN criteria ([Baccarani et al 2013](#)) defining failure of a second line treatment adapted to include discontinuation of randomized treatment as an event:

- No CHR or > 95% Ph+ metaphases at three months after initiation of therapy or thereafter
- BCR-ABL1 ratio > 10% IS and/or > 65% Ph+ metaphases at six months after initiation of therapy or thereafter
- BCR-ABL1 ratio > 10% IS and/or > 35% Ph+ metaphases at 12 months after initiation of therapy or thereafter
- Loss of CHR, CCyR or PCyR at any time after initiation of therapy
- Detection of new BCR-ABL1 mutations which potentially cause resistance to study treatment (T315I and V299L), at any time after initiation of therapy
- Confirmed loss of MMR in 2 consecutive tests
- New clonal chromosome abnormalities in Ph+ cells: CCA/Ph+: at any time after initiation of therapy

- Discontinuation from randomized treatment for any reason* (Note that Reason for treatment discontinuation="completed" doesn't indicate a premature treatment discontinuation)

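### From week 16 no scheduled PCR falls in the 4-6 week window that confirms loss of MMR, so a patient who stays on treatment and misses the extra sample is, barring narrow exceptions, censored as event-free for duration of MMR

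*Combined protocol and SAP*

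**What the plan says.** The references are to addendum 1.0 of the SAP (14-Oct-2020), the latest SAP text shown in full.

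Section 5.4.1 defines loss of MMR as a BCR-ABL1 ratio above 0.1% IS, with a rise of at least 5-fold from the on-treatment nadir, replicated on the same sample. It then adds: "Loss of MMR must be confirmed by a subsequent sample analysis within 4-6 weeks showing loss of MMR". An intervening result at or below 0.1%, or with a smaller rise, cancels the confirmation. The section does not say what happens when the confirming sample is late or was never drawn.

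Two routes need no repeat PCR:

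- "However, an assessment indicating (unconfirmed) loss of MMR will be considered as confirmed loss of MMR if the patient had loss of CHR" or of CCyR after MMR was achieved. Section 5.4.2 restricts this: "Loss of CCyR must have led to treatment discontinuation because of lack of efficacy". Section 5.4.3 sets the same condition for CHR. Section 2.7.1.2 also notes that "bone marrow aspirate for cytogenetic analyses will be performed as long as subjects have not achieved MMR".
- "CML-related death or progression to AP or BC will be considered as confirmed loss of MMR in any case", provided it occurred on treatment.

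Under section 2.7.1.1, duration of MMR ends at "the earliest date of confirmed loss of MMR, progression to accelerated phase (AP)/blast crisis (BC), or CML-related death". Without such an event, section 2.7.3 says "the duration will be censored at the last molecular assessment (PCR) date on treatment". Section 5.4.4 lists "Confirmed loss of MMR in 2 consecutive tests" as a treatment-failure criterion and does not repeat the interval.

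**The concern.** The definition depends on a sample that the assessment schedule does not supply. Whether a sustained molecular loss becomes an event then depends on whether an extra visit took place inside a two-week window, not on the course of the disease. When it did not, the patient stays in the Kaplan-Meier risk set as a responder through every later losing PCR. The error always lengthens duration of MMR.

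There is a smaller effect elsewhere. Confirmed loss is a treatment-failure event, and anyone who meets a failure criterion before week 96 is a non-responder for the key secondary endpoint (section 2.6.1). Suppose two patients on treatment have the same scheduled PCRs, lose MMR in mid-study and are back at or below 0.1% by week 96. They can be classified differently for TTF and for week 96 MMR, solely because one had a repeat in the window.

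**Working it through.** The plan states no rate for loss of MMR and no rate of missed confirmation, so it has no figure of its own to reproduce on this point.

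**Step 1: schedule against window.** Table 2-1 places PCRs at weeks 4, 8, 12, 16, 24, 36, 48 and so on, with target day 7k + 1. The window is 28 to 42 days.

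| Adjacent PCRs | Target days | Gap | In window? |
|---|---|---|---|
| 4-8, 8-12, 12-16 | 29, 57, 85, 113 | 28 days (4 weeks) | yes |
| 16-24 | 113, 169 | 56 days (8 weeks) | no |
| 24-36 and each later pair | 169, 253, ... | 84 days (12 weeks) | no |

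From week 4 to week 96 there are 10 adjacent pairs. Three qualify, and none of the seven from week 16 onwards does. Confirmation there needs an unscheduled sample, or an end-of-treatment sample that happens to fall in the window.

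**Step 2: one constructed patient.** First MMR is at week 24 (day 169). PCRs at weeks 48, 60 and 72 (days 337, 421, 505) all exceed 0.1% with at least a 5-fold rise. There is no sample at weeks 52-54 or 64-66, and none of the exceptions applies. With the section 2.7.1.1 formula:

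- Loss dated at week 48: (337 - 169 + 1)/7 = 24.1 weeks, event.
- Literal rule, with week 72 the last on-treatment PCR: (505 - 169 + 1)/7 = 48.1 weeks, censored.

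**Step 3: size, by assumption.** Let L be the true proportion losing MMR by a given time and c the proportion of losses with a valid repeat. Take a constant hazard and no other censoring.

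- If unconfirmed losers stay at risk, reported retention = 1 - L × c.
- If they leave the risk set at the losing PCR, only a fraction c of the hazard is counted, so reported retention = (1 - L)^c.

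| True retention | c | 1 - L × c | (1 - L)^c |
|---|---|---|---|
| 80% | 0.90 | 1 - 0.20 × 0.90 = 82% | 81.8% |
| 80% | 0.70 | 86% | 85.5% |
| 80% | 0.50 | 90% | 89.4% |
| 90% | 0.90 | 91% | 91.0% |
| 90% | 0.70 | 93% | 92.9% |
| 90% | 0.50 | 95% | 94.9% |

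A Kaplan-Meier simulation with 12-weekly PCRs over 96 weeks agrees. For true retention of 80% and c of 0.90, 0.75 and 0.50, it gave 0.820, 0.850 and 0.900 when unconfirmed losers stayed at risk, and 0.819, 0.847 and 0.895 when they were censored at the losing PCR.

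**The case against.** **Exceptions exist.** A reader might infer that loss can never count without the timed repeat. The documents do not support that, because section 5.4.1 gives the two routes set out above. They are narrow, however. Loss of CHR or CCyR must have led to discontinuation for lack of efficacy, and marrow cytogenetics are not routinely continued once MMR is reached. A purely molecular loss in a patient who stays on treatment has no other route.

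**Stopping and switching.** It is tempting to add patients who stop or switch and whose later PCRs all show loss. That does not fit the plan. Section 2.1.1 excludes assessments after end of treatment or treatment failure from these analyses, and switching itself requires documented treatment failure (section 1.1). These patients are censored because discontinuation is not an event for duration of MMR. The 4-6 week window is not the main cause, and some of them will meet an exception.

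**Section 5.4.4.** A reader might see a second, conflicting definition there. The wording can equally be read as the section 5.4.1 term, with the first and the confirming sample as the two tests. If it were read as having no time limit, consecutive scheduled losses would be treatment failure and the data would be cut there. The patient would still be censored rather than counted as an event, so the right-hand column above shows the approximate size.

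**Importance.** Duration of MMR is a non-confirmatory secondary endpoint, summarised by arm without a planned comparison. A patient out of MMR at week 24 or week 96 is a non-responder whether or not the loss is confirmed. Nothing in the documents shows a difference between arms. The body of the protocol is not in the part shown, so it may contain a repeat-sampling instruction. Such an instruction would make missed samples rarer but would not say how to analyse one. These limits stand and restrict the point to what is claimed here.

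**Conclusion.** The point holds for patients who remain on treatment, whose loss is first seen at week 16 or later, who have no sample in the window and who meet no exception. Read literally, sections 5.4.1 and 2.7.3 together never count their loss, and duration of MMR is biased upwards. The gap in the schedule is a fact of the documents. The size is an assumption: about 2 to 10 percentage points of retention for a true loss of 20%, and 1 to 5 points for 10%, as the share of losses with a valid repeat falls from 90% to 50%.

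The effect on TTF and week 96 MMR is confined to patients who stay on treatment. For week 96 MMR they must also have regained MMR by that visit. The documents support neither a claim that the primary result is compromised nor a claim that one arm is favoured.

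**What to change.** 1. For duration of MMR, state in section 5.4.1 that if no sample falls in the 4-6 week window, the next available on-treatment PCR confirms the loss. This applies provided no assessment in between shows a ratio at or below 0.1% or a rise below 5-fold. Date the event at the first losing sample.
2. Add a sensitivity analysis of duration of MMR that counts an unconfirmed loss at the last on-treatment PCR as an event when treatment then stops for lack of efficacy or the patient switches. Item 1 does not reach these patients.
3. State that the section 5.4.4 criterion refers to the section 5.4.1 definition of confirmed loss.
4. Leave treatment failure unchanged in the primary and key secondary analyses. It forms part of both estimands, and the current SAP is dated after the primary database lock. Apply the next-available-PCR rule to TTF and week 96 MMR only as a sensitivity analysis, specified before the 96-week analysis.

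The cost is SAP wording and a revised derivation on PCRs already collected. Duration of MMR becomes slightly less favourable. Some dependence on extra samples remains: a loss at week 36 that has reversed by week 48 is confirmed only if a sample was drawn in between.
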